Sports drinks like Gatorade, Vitamin water, Powerade (do NOT include diet)	0	0	0	0	0	0	0	0	0	0	0	0	0
Diet fruit, energy, or sports drinks like diet cranberry drink, Red Bull Sugarfree, Powerade Zero	0	0	0	0	0	0	0	0	0	0	0	0	0
Diet soda or pop like Diet Coke or Sprite Zero	0	0	0	0	0	0	0	0	0	0	0	0	0
Regular soda or pop like Coke, Pepsi, Sprite, Sunkist, grape soda (do NOT include diet)	0	0	0	0	0	0	0	0	0	0	0	0	0
Pre-sweetened coffee like mocha or Frappuccino (do NOT inlcude diet or plain coffee you add sugar to)	0	0	0	0	0	0	0	0	0	0	0	0	0
Unsweetened coffee (black or with milk)	0	0	0	0	0	0	0	0	0	0	0	0	0
Pre-sweetened tea like Arizona or Snapple (do NOT include diet or plain tea you add sugar to)	0	0	0	0	0	0	0	0	0	0	0	0	0
Unsweetened or diet tea like plain tea, diet Arizona, diet Snapple	0	0	0	0	0	0	0	0	0	0	0	0	0
Plain or flavored milk (do NOT include milk in cereal)	0	0	0	0	0	0	0	0	0	0	0	0	0
Unsweetened bottled or tap water (including sparkling)	0	0	0	0	0	0	0	0	0	0	0	0	0

BE SURE TO ANSWER THESE QUESTIONS FOR ALL BEVERAGES YOU DRANK

2

Hydrate Philly Water Fountain Observation Cheat Sheet

- 1. Arrive at recreation center. Find site leader and ask for today's program attendance.
- 2. (Intervention sites only) Record 'challenge game' and 'program bottle count'.
- 3. Take photos of water source at 10 feet and close up.
- 4. (If time allows) test time to fill bottle/cup from bottle filler and/or spigot.
- 5. Immediately before observation period begins, record flow meter reading and take photo.
- 6. As observation period begins, count initial tally of total site visitors.
- 7. Complete observation period.
- 8. Immediately after observation period ends, record flow meter reading and take photos.
- 9. If you did not do so earlier, test time to fill bottle/cup now.
- 10. Text photo of completed observation form to [name] at [contact].

Hydrate Philly Water Fountain Observation Protocol

Overview of Observation Design

- 1. All 28 study sites will receive 5 observations (1 each weekday) lasting 30 minutes each (see Appendix A for schedule).
- 2. Observations will occur over 2-3 weeks by a single RA at each site. RAs will train to reliability using a gold standard measurement and a 2nd RA will conduct intermittent 2nd observations overlapping with the 1st RA for inter-rater reliability calculation purposes.
- 3. Intervention and control matched pair sites will be observed at the same time period.

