- 4. If there are 2 hydration stations or water fountains at the recreation center, observations will occur at the location where the flow meter is installed (see Appendix B for list).
- 5. Observations will overlap with the post-measurement period (i.e., same time as flow meter readings, attendance, and tally of water bottles, reusable bottles, and sugary drinks are being reported by site leaders).

6.

Observation Protocol

- 1. Arrive at least 15 minutes before observations are scheduled to begin. It is very important all observations start on schedule. Do not begin observing early; begin at the scheduled time -- otherwise it can affect the results. Prior to observations beginning, these pieces should be started:
 - a. # Program Participants on Site (ask site leader for today's attendance)
 - b. 2 Photos of the fountain
 - c. "Before" photo of the flow meter or bottle counter (immediately before obs. period starts)
 - d. # Total Site Visitors (immediately as obs. period starts)
- 2. Sit or stand in an area close to the water source. Choose a spot where you can best observe the water flow coming from the water source. Do not sit so close as to be an obstruction. If needed, you can walk around a little bit to observe the other drinks that site visitors are consuming.
- 3. Complete the observation form. Use one observation form per 30 minutes long observation. If you are paired with another volunteer during your shift, you each should complete your own observation form.
 - a. **Intervention Only:** For intervention sites only, complete:
 - i. **Challenge Game:** Circle Y or N for whether the "Weekly Water Challenge" game poster is hanging up somewhere in the center
 - ii. **Program Bottle Count:** The number of "Hydrate Philly" branded water bottles that were seen in possession by children and adults at summer camp at the recreation center (not just from your observation post).
 - b. **Photos:** Please take two photos before each observation period 1) the water source at a distance of approximately 10 feet; and 2) water source basin close-up. In the first photo, we would like to see if there are any obstructions near the water source. In the second we would like to see if there is

- any dirt, trash, etc. in the water source basin that could impact consumption. (If you are paired with another volunteer on your shift, only one of you needs to take and send photos)

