- f. Time to fill bottle: Use a stopwatch to time how long it takes to completely fill 1) your small cup from the spigot and 2) your 20oz bottle from the bottle filler (intervention sites only). If two staff members are available, this measurement should be performed with your observation partner such that one partner holds the stopwatch and another partner fills the bottle and gives start/stop directions to the timer The measurement should be performed twice with each measurement partner swapping roles of timer versus bottle filler. The timer will record the measure on their observation form (so after the roles are switched the other person will be able to record their time on their own observation form). The measure should be repeated 3 times to obtain a reliable estimate.
 - i. Test bottle fill time either before you record the first flow meter reading or after you record the flow meter reading at the end of the observation period, so the bottle testing does not affect water usage (and therefore flow meter reading) during the observation period.
- g. Tally of program participants and other site visitors using water sources:
 - i. Count each time a water source is used as a separate tally. (i.e. if a man approaches a water source and drinks directly from the spout and then fills up his water bottle, count him both under sips and under bottles. Or if a girl takes a sip and then returns)
 - 1. Use a stop watch to time how long (in seconds) the visitor sips from the spigot, or how long water flows from the bottle filler into their bottle. Count only the time in which the visitor is actually drinking water or there is water touching his/her lips.
 - 2. For filled bottles, check 'R' if the visitor is using a reusable bottle. Do not count disposable cups or single use bottles.

- 3. If visitors are drinking from the fountain back-to-back, and you do not have enough time to record and restart stopwatch between visitors, then pause the stopwatch in between visitors and capture overall time for that group of visitors. Record this number of seconds, then in parentheses to the right of the value, record the number of visitors who drank during that measure; e.g. 25.61 sec. (4)
- h. **Other Beverages Observed:** Tally a count of other beverages by their type for anyone within view of your observation post. Do not count beverages that are clearly not meant to be consumed (e.g. children returning unused milk cartons at the end of lunchtime).

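### Observers' bottle-fill tests, done in the intervention arm only, are counted in the two-week metered water total at post

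*Protocol*

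**What the plan says.** The Measures section defines the primary outcome as each center's total gallons from its hydration station (or existing fountain, in control centers). Research staff read the flow meter at the start and end of each two-week period.

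Appendix E then adds fountain observations at post:

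- **Visits:** "All 28 study sites will receive 5 observations (1 each weekday) lasting 30 minutes each".
- **Staffing and span:** "Observations will occur over 2-3 weeks by a single RA at each site", with a second observer present intermittently for reliability checks.
- **Outlet:** where a center has two outlets, "observations will occur at the location where the flow meter is installed".
- **Timing:** "Observations will overlap with the post-measurement period (i.e., same time as flow meter readings, attendance, and tally of water bottles" and the other site-leader tallies).
- **Fill test (item 3f):** a small cup from the spigot at all sites, and "2) your 20oz bottle from the bottle filler (intervention sites only"). "The measure should be repeated 3 times to obtain a reliable estimate".
- **Safeguard (item 3f.i):** the test is done before the first or after the last meter reading of the visit, "so the bottle testing does not affect water usage (and therefore flow meter reading) during the observation period".

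**The concern.** Item 3f.i shows that the authors knew test fills move the meter, but it protects only the 30-minute observation interval. A fill made just before or just after that interval still lies between the opening and closing two-week readings, and it is those readings that give the primary outcome. The protocol neither deducts this water nor moves the tests outside the two-week window.

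Water drawn equally in both arms would add noise and a common shift. The 20-oz fills are scheduled by arm, so they raise the intervention total and leave the control total unchanged. There are no observation visits at baseline, so adjusting for the baseline reading cannot remove the excess. The same gallons are the numerator of the ounces-per-person estimate, which carries the same bias.

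**Working it through.** The protocol gives no volume for the test water, so there is no stated figure to reproduce.

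**Inputs from the protocol**
- Bottle volume: 20 oz, intervention sites only (Appendix E, item 3f)
- Fills per visit: 3 (item 3f)
- Visits per site: 5, over 2 to 3 weeks (Appendix E, Overview, items 1 and 2)
- Metered window: 2 weeks (Measures)
- 128 oz per gallon

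**Assumptions**
- One observer, every test completed.
- Bottle-filler water passes through the meter, as the primary outcome definition implies.
- Between 3 and 5 visits fall inside the window. Five fit if all visits are made in those two weeks. If the visits are spread evenly over three weeks, 5 × 2/3 = 3.3 fall inside.

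**Formula:** excess gallons per intervention center = visits in window × fills per visit × 20 / 128.

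| Case | Ounces | Gallons |
|---|---|---|
| One visit, 3 fills | 3 × 20 = 60 | 0.47 |
| 3 visits in window | 3 × 60 = 180 | 1.41 |
| 3.3 visits (even spread over 3 weeks) | 3.33 × 60 = 200 | 1.56 |
| 4 visits | 4 × 60 = 240 | 1.88 |
| 5 visits | 5 × 60 = 300 | 2.34 |

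**Paired visits.** Item 3f has two partners swap roles and repeat the test, which gives 6 fills if each completes the set of three. One paired visit out of five gives (4 × 3 + 6) × 20 = 360 oz = 2.81 gal. All five paired gives 5 × 6 × 20 = 600 oz = 4.69 gal, although second observations are meant to be only intermittent.

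**Relative size.** The protocol gives no expected two-week volume. The totals below are assumed, for illustration only.

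| Assumed two-week total | 1.41 gal | 2.34 gal |
|---|---|---|
| 25 gal | 5.6% | 9.4% |
| 50 gal | 2.8% | 4.7% |
| 100 gal | 1.4% | 2.3% |
| 200 gal | 0.7% | 1.2% |
| 400 gal | 0.35% | 0.59% |

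The 871 in the Appendix B form is an example meter reading, not a two-week volume, so it cannot serve as the denominator.

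**Per person.** With an assumed 28 children a day for 10 days (280 attendances), the excess is 180/280 = 0.64 oz to 300/280 = 1.07 oz per attendance.

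**The case against.** The strongest reply is that the effect may be trivial and is correctable from data already collected. Without an expected volume, standard deviation or effect size in the protocol, no harm to any conclusion is shown. The Appendix F form carries the date and three timing fields for the bottle, and each observer completes a separate form. Completed fields × 20 oz would therefore recover most of the volume, and a deduction rule could sit in a statistical analysis plan that is not available here. The Measures section also concedes that some metered water is not consumed, giving cup rinsing as an example.

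The amount is uncertain in both directions. Step 4 of the cheat sheet makes the test conditional on time, and the proposed daily schedule starts travel from the first two sites the minute observation ends, so some tests may be skipped. The number of visits inside the window is inferred. Paired visits push the volume up. The meter's position relative to the bottle filler is not described, and the cancelling of cup fills is also assumed, since no cup size is given.

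Much of this stands as a limit on the size, and 1.4 to 2.3 gal is a base case, not a pair of bounds. It does not remove the problem. Step 9 of the cheat sheet picks up tests missed earlier: "If you did not do so earlier, test time to fill bottle/cup now". The remark on non-consumption use concerns ordinary use in either arm, not water that study staff draw on a schedule that differs by arm. The point also does not depend on what an analysis plan may contain: it arises from a field procedure fixed in this protocol, whose safeguard covers the wrong interval. Fills that are not timed, and the cup volume, can be captured only on site.

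**Conclusion.** The concern holds. Followed as written, the protocol adds study-staff water to the primary outcome in the intervention arm only and at post only. The base case is 1.4 to 2.3 gal per intervention center, assuming one observer, all tests completed, three to five visits inside the window, and filler water passing through the meter. Paired visits raise the figure and skipped tests lower it. The direction is known and favours the intervention. The bias is probably small, but the protocol gives no volume against which to confirm that. It is worth correcting because it is systematic and easily removed, not because it is likely to overturn the result.

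**What to change.** Add to item 3f and the Appendix F form a count of all test fills, cup and bottle, by each observer, and state the cup size. Add one instruction: sum the volume of test fills made between the opening and closing two-week readings and subtract it from the center's total, in both arms, before analysis and before computing ounces per person. The bottle timing fields and the date are already on the form, so the burden is slight. With complete counts, the arm-specific excess falls to zero.

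Count fills instead of taking extra meter readings around each test. At about 0.47 gal per visit, the change may not show if the meter is read in whole gallons, as in the Appendix B example.

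The alternative is to do the fill tests before the opening or after the closing two-week reading. That needs no deduction but gives up fill times measured on the same day as the observations. If data have already been collected, completed timing fields × 20 oz, restricted to dates inside the window, give a workable retrospective deduction for the bottle fills.

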Appendix A – RA Observation Schedule

Proposed Daily Schedule						
Time	Agenda					
10:30a	Arrive site 1					
10:45a to 11:15a	Site 1 observations					
11:15a to 12p	Travel from site 1 to site 2					
12p	Arrive site 2					
12:15p to 12:45p	Site 2 observations					
12:45p to 1:30p	Travel from site 2 to site 3					
1:30p	Arrive site 3					
1:45p to 2:15p	Site 3 observations					
2:15p to 2:30p	Wrap up for day					

Appendix B – Description of water fountain that will be observed

Site ID	No. of	Fountain	Location to Observe
	Fountain	Type	
1806	2?	Elkay	ground floor, between the bathrooms near office
1610	2	Elkay	in lobby outside of auditorium
1812	2	Elkay	in main lobby
1208	2?	Elkay	inside the gym, as you enter, to the left
1216	1	Elkay	only 1 fountain
1226	1	Elkay	only 1 fountain
1402	1	Elkay	only 1 fountain
1618	1	Elkay	only 1 fountain
1620	1	Elkay	only 1 fountain
1624	1	Elkay	only 1 fountain
1728	1	Elkay	only 1 fountain
1822	1	Elkay	only 1 fountain
1604	2	Elkay	up steps in main lobby across from gym
1314	2	Elkay	upstairs across from office
2811	2	Fountain	as you enter the building, to the right, near office
2307	2	Fountain	in lobby, next to the vending machines
2315	2	Fountain	on main floor, in hallway leading to computer room
2223	2	Fountain	outside of the main office, near the bathrooms
2225	1	Fountain	only 1 fountain
2227	1	Fountain	only 1 fountain
2205	1	Fountain	only 1 fountain
2409	1	Fountain	only 1 fountain
2819	1	Fountain	only 1 fountain
2821	1	Fountain	only 1 fountain
2803	1	Fountain	only 1 fountain
2413	1	Fountain	only 1 fountain
2729	1	Fountain	only 1 fountain
2317	1	Fountain	only 1 fountain

Observer Name:	General Information								
Site Name:	Intervention Only: Challenge Game: Y N	# Program Partic. on Site During Obs. Period:	# Total Site Visitors During Obs. Period:						
Date:	Program Bottle Count:								
Obs. Start Time:	Obs. End Time:	Flow meter @ Start:	Flow meter @ End:						
Time to fill small cup from spigot	  ::	Time to fill 20oz bott	 le from bottle filler: (Intervention only)						
1 sec. 2	sec. 3 sec.		2sec. 3sec.						
Observations									
Tally Who Drank from Observed Water Source:									
Sips:		Filled Bottles/Cups	(single-use containers not marked R):						
sec sec	sec.	sec. □R							
sec sec	sec.	sec. □R	sec. □R sec. □R						
sec sec	sec.	sec. □R	sec. □R sec. □R						
sec sec	sec.	sec. □R	sec. □R sec. □R						
sec sec	sec.	sec. □R	sec. □R sec. □R						
sec sec	sec.	sec. □R	sec. □R sec. □R						
sec sec	sec.	sec. □R	sec. □R sec. □R						
sec sec	sec.	sec. □R	sec. □R sec. □R						
sec sec	sec.	sec. □R	sec. □R sec. □R						
sec sec	sec.	sec. □R	sec. □R sec. □R						
sec sec	sec.	sec. □R	sec. □R sec. □R						
sec sec	sec.	sec. □R	sec. □R sec. □R						
sec sec	sec.	sec. □R	sec. □R sec. □R						
Tally Other Beverages Observ	ved:								
Water in Reusable Bottle:	Bottled Water (Single Use):	Milk (Plain):	Milk (Flavored):						
	T								
Diet Soda/Diet Tea:	100% Juice:		Soda:						
Other Sugary Beverages:	Coffee:		Unknown:						
List of Other Sugary Beverages (c Sunny-D, Capri-Sun, sweet tea):	e.g. lemonade, milkshake,		inventory of beverages available or for sale nearby, tain, signage re: water or other beverages):						

Hydration Station Maintenance Needs

Tracking the maintenance needs of water fountains and hydration stations over the course of six months

* Required

	O'	
1.	Site Nank o	ame * only one oval.
		CB Moore
		Chew
		Christy
		Cohocksink
		Cruz
		East Poplar
		Feltonville
		FJ Myers
		Gambrel
		Gathers
		Glavin
		Hillside
		James Wright
		Kingsessing
		Lee Cultural
		Lonnie Young
		Mander
		McIlvain
		McVeigh
		Morris Estate
		Olney
		Рара
		Penrose
		Rivera
		Roosevelt
		Smith
		Tustin
		Vogt

2.	Person filling out form. *
	Mark only one oval.
	Caretaker
	Recreation Leader
	Other:
3.	How often in the past week have you had to remove gum, seeds, or other food from the fountain/hydration station(s)? *
	Mark only one oval.
	Every Day
	3-5 times
	Once or twice
	Never
	Never
4.	How often in the past week have you had to remove graffiti from the fountain/hydration
	station(s)? *
	Mark only one oval.
	Every Day
	3-5 times
	Once or twice
	Never
5.	How often in the past week have you had to remove dirt/dust from the fountain/hydration station(s)? *
	Mark only one oval.
	Every Day
	3-5 times
	Once or twice
	Never
6.	How often in the past week have you had to remove trash from the fountain/hydration
	station(s)? * Mark only one oval.
	·
	Every Day
	3-5 times
	Once or twice
	Never

7. How often in the past week have you had to clean the fountain/hydration station(s) of blood/mucus? *	
Mark only one oval.	
Every Day	
3-5 times	
Once or twice	
Never	
Ideaci	
8. How often in the past week have you observed the fountain/hydration station(s) to be clogged? (Water stuck in the basin, not draining or slowly draining) * Mark only one oval.	
Every Day	
3-5 times	
Once or twice	
Never	
9. How often in the past week have you observed the fountain/hydration station(s) to be flooded? (Water overflowed, not due to children spilling) *	
Mark only one oval.	
Every Day	
3-5 times	
Once or twice	
Never	
10. How often in the past week have you needed to wipe down the fountain/hydration station? (general cleaning) * Mark only one oval.	
Every Day	
3-5 times	
Once or twice	
Never	
11. How much time does it typically take to maintain the fountain/hydration station? *	
12. Have you experienced any issues with maintenance of the fountain/hydration station? If so, explain. *
